7.5 REPORTING OF ADVERSE EVENTS

In order to ensure prompt reporting of adverse events, all adverse events (as well as all related study data) must be entered into the WebDCU™ within five working days following the completion of the Baseline, Treatment, and Day-7 or discharge (whichever occurs first) trial phases. All serious adverse events (SAEs) must be reported on the WebDCU™ within 24 hours of the study site staff first being made aware of its occurrence. The 24-hour reporting requirement for SAEs applies to all study phases. The investigators are required to provide relevant information, including description of the adverse event, date/time of onset and resolution, severity and seriousness, action taken, and suspected relationship to the study drug. Similarly, all adverse events of respiratory compromise, whether serious or not, must be reported in WebDCU™ and the relevant CRF completed within 24 hours of the study site staff first being made aware of its occurrence.

Reporting of respiratory compromise, as well as any serious or life-threatening adverse event, will trigger notification of the event to the Project Manager (PM), the independent MSMs, and appropriate members of the Executive Committee (EC). The MSMs will conduct an independent review of each of these events to determine its relatedness to the study drug along with other elements, and to confirm or exclude the diagnosis of ARDS in cases of respiratory compromise. Within 72 hours of receipt of these events for review, the MSMs will enter into the trial's database their opinion regarding whether the adverse event is, in fact, serious, and if it is unexpected and related to the study drug. If the MSMs believe all three elements are present in the SAE, an expedited safety report (MedWatch) will be filed with the FDA within the stipulated regulatory guidelines: for fatal or life-threatening SAEs, no later than 7 calendar days after the sponsor's initial receipt of information, and for SAEs outside those categories, no later than 15 calendar days after the sponsor determines that the event requires expedited reporting (21 CFR 312.32(c)(1)). If the study site investigator(s) and the MSMs are not in agreement on these issues and fail to resolve their disagreement after direct communication, the opinion of the MSMs will be considered as the final adjudication. When a MedWatch Report is filed with the FDA, a copy of the MedWatch Report (or a link to a secure file in the trial database) will be sent to the DSMB through the NINDS liaison.

Each clinical site PI and primary Study Coordinator will receive an email notification that a MedWatch Report has been filed with FDA. The email notification will contain instructions for accessing the report. It is the responsibility of each clinical site PI to file these reports with his/her IRB in compliance with their institution's local requirements. After the submission of the initial MedWatch Report, the principal investigator at the corresponding clinical site will be responsible for obtaining follow-up information about the event and reporting it in the WebDCU™.

7.6 MONITORING OF ADVERSE EVENTS

Two independent Medical Safety Monitor (MSMs), appointed in consultation with the NINDS program director, will monitor the study with regard to safety on an ongoing basis to identify any safety concerns. The MSMs will review all cases of respiratory compromise and all SAEs to determine whether they are related to study drug administration, and to ascertain the diagnosis of ARDS in cases of respiratory compromise. They will communicate with the investigators

for any questions or clarifications regarding an event. Periodically throughout the study, the EC and the MSMs will review reports on the incidence rates of all reported adverse events, whether serious or not, with particular attention to SAEs, respiratory compromise including ARDS, and mortality during the first 7 days of hospitalization (or until discharge, whichever is earlier). Should such monitoring uncover issues that may threaten subject safety (e.g. unexpectedly high rate of adverse events), the study statistician and principal investigator will prepare a report to be submitted to the DSMB for their review and further actions to be taken, if any.

Two statistical reports will be generated semiannually (unless requested at a more frequent interval by the MSMs or DSMB) – an open report to be distributed to the Executive Committee and MSMs, and a closed report to be distributed only to the NINDS-appointed DSMB. Each semi-annual report will provide cumulative summary statistics on enrollment, subject status in the study, baseline characteristics, protocol violations, safety data (including a summary of the most frequent and most serious adverse events, a summary of all MedWatch Reports, and a listing of all subjects who were terminated from the study and the reason for termination), and data management/quality information. The statistics will be provided for the overall study. For the closed report only, the statistics will also be provided by partially blinded treatment group (A vs. B). If the DSMB wishes to be completely unblinded for these reports, a sealed identification envelope will be provided to the NINDS DSMB liaison; this envelope can be opened at the discretion of the DSMB. An annual report will be submitted to the FDA and Health Canada.

7.7 STOPPING RULE

The occurrence of ARDS will be continuously monitored during the course of the trial, in order to facilitate thorough review of the data by the DSMB and to stop enrollment into the trial if sufficient evidence of imbalance in the rate of ARDS exists. The NINDS-appointed DSMB recommended that recruitment be stopped if the difference in the number of confirmed ARDS cases between the groups is 5 at any time during the recruitment of the first 40 subjects; 10 at any time during the recruitment of subjects 41-80; 12 at any time during the recruitment of patients 81-120; or if the difference in the number of confirmed ARDS cases between the groups is statistically significant after 40, 80, or 120 subjects have completed the in-hospital phase based on a Pocock-adjusted, one-sided, 0.05 alpha level. This one-sided hypothesis is consistent with our concern for patient safety, wherein early termination is considered only if ARDS incidence is higher on the DFO arm than on the control arm.

These analyses will be based on the occurrence of confirmed ARDS cases (according to the Berlin criteria) thought to be at least possibly related to study drug. The ARDS cases will be reviewed on an ongoing basis throughout the trial by the MSMs (who will adjudicate all cases together to provide a consensus opinion about the diagnosis, severity, and possible plausible causes other than the study drug). The DSMB will be notified of each individual ARDS occurrence upon confirmation by the MSMs, per their request. Given that a common definition for the diagnosis of ARDS will be used, we do not anticipate much discrepancy between the site's assessment and the MSM's assessment. However, in the event of disagreement, the MSM's assessment will be used.

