All adverse events or complications will be submitted electronically via the WebDCU™ system and assigned to a system-organ class and preferred term using MedDRA coding dictionary. The number and percent of all adverse events will be summarized for each treatment arm by event type. Tables will be generated to detect any clinically significant laboratory abnormalities in change of values from baseline to end of the last infusion. We anticipate no missing safety data regarding adverse events, since patients will remain hospitalized and closely monitored until day-7 or discharge (whichever is earlier). The cumulative incidences of each AEOSI, as well as mortality, will be compared via 95% confidence intervals. Mortality will also be assessed via the log rank test for comparing survival curves.

Analysis of the safety data regarding the occurrence of ARDS will be carried out continuously throughout the trial by the unblinded study statistician, who will notify the EC and DSMB if recruitment must be stopped. The DSMB will be notified of each individual ARDS occurrence upon confirmation by the MSMs, per their request. Analysis of other safety data by the DSMB will occur semiannually (or more frequently if requested by the DSMB). If any of these analyses reveal serious emerging concerns, the EC, in consultation with the DSMB, may implement modifications to assure safety as necessary. Apparent, consistent and persistent evidence of net harm that tends to overwhelm any benefit may allow for premature termination of the study.

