9.3 ONGOING SAFETY MONITORING DURING THE STUDY

Two independent Medical Safety Monitors (MSMs), appointed in consultation with the NINDS program director, will monitor the study with regard to safety on an ongoing basis to identify any safety concerns. As mentioned above in section 7.6, the MSMs will review all SAEs and cases of respiratory compromise and determine whether they are related to study drug administration, and will communicate with the investigators for any questions or clarifications regarding an event. Periodically throughout the study, the EC and the MSMs will review reports on the incidence rates of all reported adverse events, whether serious or not, with particular attention to SAEs, ARDS, and mortality during the first 7 days of hospitalization (or until discharge, whichever is earlier). Should such monitoring uncover issues that may threaten subject safety (e.g. an unexpectedly high rate of adverse events), the study statistician and principal investigator will prepare a report to be submitted to the DSMB for their review and further actions to be taken, if any.

Analysis of the safety data regarding the occurrence of ARDS will be carried out continuously throughout the trial by the unblinded study statistician, who will notify the EC and DSMB if recruitment must be stopped (please refer to section 7.7 for the stopping rule). The DSMB will be notified of each individual ARDS occurrence upon confirmation by the MSMs, per their request. Analysis of the overall safety data by the DSMB will take place periodically throughout the trial. The first analysis is planned after the first 40 subjects have completed the in-hospital phase of the study. The number and timing of subsequent analyses will be determined in consultation with the DSMB as the study progresses.

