10.4 DATA AND SAFETY MONITORING PLAN

The DSMB, appointed by the NINDS and managed by the NINDS Clinical Trials group, will be responsible for the oversight of safety of trial participants, review of the safety reports, requesting additional data/information (if necessary), and advising the NINDS regarding continuation/ discontinuation of the study. The study may be modified or discontinued at any time by the NINDS, the FDA, or the Executive Committee to ensure that research subjects are protected. All ARDS cases will be monitored continuously throughout the trial by the unblinded study statistician, who will notify the EC and DSMB if recruitment must be stopped (please refer to section 7.7 for the stopping rule). The DSMB will be notified of each individual ARDS occurrence upon confirmation by the MSMs, per their request. Analysis of the overall safety data by the DSMB will take place periodically throughout the trial. The first analysis is planned after the first 40 subjects have completed the in-hospital phase of the study (day-7 or discharge, whichever is earlier). The DSMB will meet to review the accumulated safety data, with particular attention to mortality, SAEs, and adverse events of special interest (AEOSI) including ARDS, from initiation of treatment to day-7 or discharge (whichever occurs first) to ensure that there are no emerging safety concerns. Unblinding of treatment assignments will only be allowed by the Chair of the DSMB, if felt necessary, but the unblinded data will be confidentially maintained within the DSMB. Enrollment will continue with the recommendation of the DSMB, including necessary modifications, if needed, to address any safety concerns early on.

After this meeting, the DSMB will regularly meet at least once approximately every 6 months or at more frequent intervals if needed to review recruitment and safety data. Analyses of the safety data will be carried out on an ongoing basis throughout the trial, as mentioned above. All AEOSIs, all SAEs, deaths, and adverse events will be reviewed by the DSMB during their meetings. There will be no limit on the number and timing of analyses aimed at guaranteeing the safety of the patients. An apparent, consistent and persistent evidence of net harm that tends to overwhelm any benefit may allow for premature termination of the study. Please refer to section 7.7 from the pre-specified stopping rule based on the frequency of ARDS cases.

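### The numerical ARDS stopping rule in section 7.7 ends at subject 120 of 294, although the statistician is to apply it throughout the trial

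*Protocol*

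**What the plan says.** Protocol section 7.7 opens by saying that ARDS is monitored continuously during the trial, so that enrolment can be stopped on evidence of imbalance. It then gives two sets of criteria:

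- **Count differences between arms:** 5 during the first 40 subjects, 10 during subjects 41 to 80, and "12 at any time during the recruitment of patients 81-120".
- **Significance tests:** "after 40, 80, or 120 subjects have completed the in-hospital phase based on a Pocock-adjusted, one-sided, 0.05 alpha level".

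The cases counted are "confirmed ARDS cases (according to the Berlin criteria) thought to be at least possibly related to study drug". Planned enrolment is 294 (sections 3.2 and 8.4).

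Three other sections describe who applies the rule and for how long:

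- Section 8.2.2: "Analysis of the safety data regarding the occurrence of ARDS will be carried out continuously throughout the trial by the unblinded study statistician". That person notifies the EC and DSMB if recruitment must be stopped.
- Section 9.3 repeats the duty and says where the criterion is: "who will notify the EC and DSMB if recruitment must be stopped (please refer to section 7.7 for the stopping rule".
- Section 10.4: "All ARDS cases will be monitored continuously throughout the trial by the unblinded study statistician", again with a reference to 7.7.

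On later safety reviews in general, section 9.3 says: "The number and timing of subsequent analyses will be determined in consultation with the DSMB as the study progresses". Sections 8.2.2 and 10.4 add a qualitative clause, under which "net harm that tends to overwhelm any benefit may allow for premature termination of the study".

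**The concern.** The duty and the rule cover different spans. The statistician must say, at any time up to subject 294, whether recruitment must be stopped for ARDS, and is sent to 7.7 for the criterion. After subject 120, section 7.7 contains neither a count threshold nor a test. It does not say that the rule is meant to lapse there, or why.

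ARDS ended the predecessor trial and is named in the primary safety objective (section 1.1). This protocol lowers dose and duration and excludes high-risk subjects in order to reduce ARDS (section 2.1.3.2). A smaller excess than in HI-DEF, one that becomes clear only with more subjects, is therefore a case the rule should be able to handle.

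**Working it through.** **1. Coverage.** The plan's total reproduces. With a 28% rate in both arms, margin 0.12, one-sided alpha 0.10 and 80% power, n per arm = (1.2816 + 0.8416)² × 2 × 0.28 × 0.72 / 0.12² = 126.2, rounded up to 127, so 254 in all. Then 254 × 1.11 × 1.04 = 293.2, rounded up to 294. The last ARDS criterion is at 120/294 = 41%. Uncovered: 294 − 120 = 174 subjects, 174/294 = 59%.

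**2. The boundary.** A three-look Pocock rule with equal spacing at one-sided 0.05 has critical value 1.992, a nominal one-sided p of 0.0232 at each look.

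**3. A path that no rule catches.** Pooled z = (difference in proportions) / √(p(1−p) × 2/n), with p the pooled rate and n per arm. The counts are invented, and no earlier threshold is assumed to have been crossed.

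- 8 v 3 at 60 per arm: p = 11/120, z = 0.0833/0.0527 = 1.58. This is below 1.992, and the difference of 5 is below 12, so the trial continues.
- 15 v 5 at 100 per arm: z = 2.36, one-sided p = 0.009. No criterion applies.
- 22 v 7 at 147 per arm: z = 2.93, one-sided p = 0.0017 (Fisher 0.0027). No criterion applies.

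**4. How often the present rule stops.** Exact recursion over the pair (DFO cases, placebo cases): 147 per arm enrolled in pairs, outcomes known at once, count thresholds read as a DFO excess, looks at 40, 80 and 120 at 1.992. Rates are those of ARDS cases at least possibly related to study drug. All are assumptions except the HI-DEF row. DSMB discretion is not modelled. Section 7.7 does not name the test, so both pooled z and Fisher are shown. The illustration keeps the rule to 120 and adds looks at 160, 200, 240 and 280 completers at nominal one-sided 0.01.

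| DFO v placebo | Present rule, pooled z / Fisher | With added looks, pooled z / Fisher |
|---|---|---|
| 15% v 5% | 50% / 37% | 78% / 70% |
| 12% v 5% | 31% / 20% | 53% / 43% |
| 10% v 5% | 20% / 11% | 35% / 25% |
| 8% v 3% | 24% / 10% | 43% / 31% |
| HI-DEF, 6/21 v 1/21 | 97% / 95% | not needed |

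HI-DEF's 6/21 is in section 3.3. The 1/21 follows from 42 enrolled and 7 cases, 6 of them on DFO. Those rates count all ARDS, whereas 7.7 counts only cases at least possibly drug-related.

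At 15% v 5%, 28% of all trials pass subject 120 under the present rule and still finish with nominal one-sided p < 0.01 (pooled z).

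**5. Price in false stops (pooled z).** With equal ARDS rates of 5%, 10% and 16.7% in both arms, the stopping probability rises from 3.5% to 4.6%, 4.8% to 5.8% and 6.7% to 7.6%. Stopping by subject 120 is unchanged.

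**6. Gain in patients (pooled z).** Mean enrolment falls from 187 to 166 at 15% v 5%, from 251 to 241 at 10% v 5%, and from 244 to 232 at 8% v 3%. Excess cases averted = half the enrolment saved × risk difference: 21/2 × 0.10 = 1.05; 10/2 × 0.05 = 0.25; 12/2 × 0.05 = 0.30.

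**The case against.** The strongest reply is that the DSMB itself recommended these thresholds. A numerical rule for the early phase followed by board judgement is an accepted design, and it fits a signal that appeared within 42 subjects in HI-DEF. At HI-DEF rates the rule stops almost every trial.

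A reader might infer that ARDS goes unwatched after subject 120, or that any stop would then rest on the DSMB's judgement alone. The protocol does not support either. The DSMB is told of each confirmed case, meets about every six months, receives closed reports by arm that it can unblind, and has no limit on safety analyses (7.6, 9.3, 10.4). Under 7.6 the EC and the medical safety monitors review ARDS rates, and the statistician and principal investigator report to the DSMB if a threat to safety appears. Under 10.4 NINDS, the FDA or the EC may discontinue the study at any time; 10.5 adds OHRP and, for its own site, an IRB.

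Nor are the stopping shares the chance that harm would go unstopped. They compare fixed rules under assumed rates, and an active board could act well before 22 v 7.

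All of this stands, and it limits the consequence. It does not supply the missing content. None of these provisions states an ARDS criterion, and 9.3 and 10.4 name 7.7, not a later document or a DSMB decision, as the place of the rule. If the rule is meant to end at 120, the protocol does not say so.

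**Conclusion.** The gap is certain on the text: a duty to signal that recruitment must stop runs to 294 subjects, while the rule it invokes ends at 120, leaving 59% of enrolment without an ARDS criterion. It matters for moderate excesses, not for one of HI-DEF size. In the assumed moderate scenarios the present rule stops between 20% and 50% of trials by pooled z, and 10% to 37% by Fisher.

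These sizes rest on assumed rates of cases at least possibly drug-related, immediate outcomes and no DSMB discretion. Whether such rates are plausible at the reduced dose cannot be judged from the protocol. The gain from later looks is about one excess ARDS case or fewer per trial, which is modest but cheap to obtain. The point should be fixed; it does not show that subjects are left without safety oversight.

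**What to change.** The sponsor and DSMB should reconcile sections 7.7, 8.2.2, 9.3 and 10.4. Keep the rule to subject 120 as it is, and add to 7.7 pre-specified ARDS looks up to full enrolment, at a level they choose, with the overall false-stop probability stated. The looks at nominal 0.01 above are only an illustration. At nominal 0.005 the false-stop probabilities are 3.9%, 5.2% and 7.1% at common rates of 5%, 10% and 16.7%, and stopping is 72% at 15% v 5% and 35% at 8% v 3% (pooled z).

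The three-look boundary should not simply be carried on: used at seven looks (40, 80, 120, 160, 200, 240, 294), it raises the overall one-sided level from 0.05 to about 0.079. A seven-look Pocock rule would need 2.203 (nominal 0.0138) at every look, which would make the early looks harder to cross.

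If the numerical rule is meant to end at 120, the four sections should say so and state what the statistician applies afterwards.

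Cost: amendment wording and DSMB agreement, with no new data and no loss of early stopping. The downside is about 1 percentage point more false stops at nominal 0.01, so the overall level is no longer that of the three-look rule alone.

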7 ADVERSE EVENTS

7.1 DEFINITION OF ADVERSE EVENTS

Adverse events are any *untoward* medical occurrence whether or not they are considered related to the study drug. An adverse event can be any unfavorable and unintended symptom, sign, disease or clinically significant abnormal test result occurring during the study which were either not present at baseline, or if present, worsened during the study in terms of either severity or frequency. When evaluating possible adverse events, an assessment should be made regarding its seriousness, severity and temporal relationship to the administration of the study drug. An adverse event is considered serious if it is life-threatening, prolongs hospitalization, requires re-hospitalization, results in significant disability, leads to death, or requires medical or surgical intervention to prevent one of the other listed outcomes. An assessment should be made regarding the seriousness, severity and relationship to the administration of the study medication as well as to the ICH. The following factors should be considered when evaluating possible adverse events: 1) the temporal sequence from drug administration; 2) patient's response after drug discontinuation or re-introduction; and 3) severity of the event. The investigators, on the basis of their clinical judgment and guided by the following definitions, should determine the relationship of an adverse event to the study drug(s) as: definitely related, i.e. following in a reasonable temporal sequence, known to be a complication of DFO, and having no other explanation; probably related, i.e. following in a reasonable temporal sequence and not reasonably explained by the patient's clinical state or other therapies; possibly related, i.e. could have been explained by other therapies or patient's clinical state; or unlikely or not related. The severity of adverse events should be graded as mild, moderate, severe, life-threatening, or fatal.

All adverse events or complications will be entered into WebDCU™ and assigned to a system-organ class and preferred term using the MedDRA coding dictionary. Each subject must be monitored closely throughout his/her hospitalization for serious adverse events (SAEs). All adverse events (serious and non-serious) should be assessed until day-7 or discharge, whichever occurs earlier, and serious adverse events until day-90 or withdrawal of consent, whichever is earlier.

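### Section 7.7 makes the ARDS stopping trigger depend on case-level causality ratings that a randomised comparison does not need

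*Protocol*

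**What the plan says.** Protocol section 7.7 opens with the aim "to stop enrollment into the trial if sufficient evidence of imbalance in the rate of ARDS exists". It then gives the trigger: "The NINDS-appointed DSMB recommended that recruitment be stopped if the difference in the number of confirmed ARDS cases between the groups is 5" during the first 40 subjects, with limits of 10 for subjects 41-80 and 12 for subjects 81-120. One-sided Pocock-adjusted tests at the 0.05 level are added after 40, 80 and 120 subjects. The second paragraph says that these analyses rest on "confirmed ARDS cases (according to the Berlin criteria) thought to be at least possibly related to study drug".

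The MSMs review the cases. Section 7.7 asks them to "provide a consensus opinion about the diagnosis, severity, and possible plausible causes other than the study drug". It expects little discrepancy with the sites, and gives the reason: "Given that a common definition for the diagnosis of ARDS will be used". That common definition covers the diagnosis only.

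Relatedness is handled in two other places:

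- Section 7.1 has a graded scale, addressed to the sites: "The investigators, on the basis of their clinical judgment and guided by the following definitions, should determine the relationship". Its middle category is wide: "possibly related, i.e. could have been explained by other therapies" or by the patient's clinical state. The lowest category, unlikely or not related, is named but not defined.
- Section 7.5 has the MSMs enter "their opinion regarding whether the adverse event is, in fact, serious, and if it is unexpected and related to the study drug", with no graded level.

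Section 10.4 says that all ARDS cases are monitored continuously by the unblinded statistician, and refers to section 7.7 for the rule.

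**The concern.** ARDS is the named safety concern of this trial, and section 7.7 holds its only numerical stopping boundary. In a 1:1 placebo-controlled comparison, the control arm shows how much ARDS occurs without the drug. Rating the cause of each case adds no information that the comparison needs, and it can remove cases that carry the signal. ICH patients often have a competing explanation such as aspiration, so a drug effect may show only as an excess of cases that each look explicable.

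The programme's own record makes this more than theoretical. Section 2.2.2 reports two respiratory failures in Phase I that were put down to aspiration pneumonia and adjudicated as unrelated to the drug. Expert review later found that one was undiagnosed ARDS, with aspiration still plausible. Section 2.2.3 reports that 4 of the 7 HI-DEF cases had another plausible cause. The DSMB nevertheless inferred likely pulmonary toxicity from the imbalance between arms, which used all the cases.

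At stake is whether the same set of confirmed cases trips the rule or not, according to how causality is rated.

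**Working it through.** **1. The plan's figures.** The limits 5, 10 and 12 are given as a DSMB recommendation without derivation or assumed rates, so they cannot be reproduced. The HI-DEF rate in section 3.3 does reproduce: 6/21 = 28.6%. The placebo arm is taken as 42 - 21 = 21, giving 1/21 = 4.8%.

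**2. HI-DEF cases under the two ways of counting.**

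- All confirmed cases: 6 v 1, difference 6 - 1 = 5, equal to the first limit.
- Without those that had another plausible cause: 7 - 4 = 3 cases remain. Their split by arm is not given, so the difference is at most 3, below the limit.

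The Pocock boundary for three equally spaced looks at one-sided 0.05 is z = 1.992, nominal p = 0.0232. Section 7.7 does not name the test, so both usual choices are shown.

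| Counts | Pooled z, p | Fisher, p |
|---|---|---|
| 6/21 v 1/21 | 0.019 (crosses) | 0.047 (does not) |
| 3/21 v 0/21 | 0.036 (does not) | 0.116 (does not) |

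For the first row, z = (6/21 - 1/21) / sqrt[(7/42)(35/42)(2/21)] = 0.238/0.115 = 2.07.

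**3. Chance of stopping, as an assumed illustration.** Exact recursion over the pair (DFO cases, placebo cases) for 120 subjects. Assumptions: allocation in 1:1 pairs, outcomes known at once, count limits applied one-sided, looks at 40, 80 and 120. True rates are set at HI-DEF's 28.6% v 4.8%, which came from a higher dose and a longer infusion. The retained fractions are assumptions, because the protocol gives no relatedness ratings for HI-DEF. Equal retention q multiplies both rates by q. In the last row the drug excess (28.6% - 4.8%) is kept whole and only the 4.8% background is multiplied by 3/7, in both arms.

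| Cases counted | z test: by 40 / by 120 | Fisher: by 40 / by 120 |
|---|---|---|
| All | 61.7% / 97.1% | 56.1% / 95.0% |
| 6/7 in both arms | 51.4% / 93.9% | 43.0% / 89.8% |
| 5/7 in both arms | 40.1% / 88.0% | 29.2% / 80.8% |
| 3/7 in both arms | 15.9% / 63.6% | 6.9% / 46.1% |
| Excess kept, background at 3/7 | 66.8% / 99.1% | 54.9% / 98.0% |

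At half the DFO rate (14.3% v 4.8%, assumed), stopping by 120 with the z test is, in the same order, 47.2%, 40.5%, 34.0%, 20.7% and 59.2%.

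**4. Cost of counting all cases.** False stopping by subject 120 when both arms share the rate 7/42 = 16.7%:

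| Cases counted | z test | Fisher |
|---|---|---|
| All | 6.7% | 4.9% |
| 6/7 | 6.0% | 3.9% |
| 5/7 | 5.4% | 3.0% |
| 3/7 | 4.1% | 1.4% |

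At a 10% common rate (assumed), the z-test figures are 4.8% with all cases, 4.1% at 5/7 and 3.2% at 3/7.

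**The case against.** The strongest reply is that nothing here conflicts. The second paragraph of section 7.7 defines the event that the first paragraph counts. This stands. A reader might infer that the DSMB set its limits for unfiltered cases and that the protocol then changed the unit. The document does not show this, because it gives no basis for 5, 10 and 12.

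The second reply is that asking for at least possible relatedness presupposes a graded scale, and section 7.1 has the only one. Under it, a case that the patient's condition could explain is still possibly related and still counts. The ungraded wording in section 7.5 serves expedited reporting, and HI-DEF filed such a report for an event rated only possibly related (section 2.2.3). Finer instructions to the MSMs may also sit in a manual or an SAP that is not shown. Most of this stands, and a missing cross-reference alone would be a small matter. It does not settle how a case counts once the MSMs have recorded another cause, and the Phase I adjudication shows that such cases have been rated unrelated. That adjudication came before the ARDS diagnosis, so it indicates the risk and is not proof of practice.

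Third, a reader might take the fall to 15.9% by subject 40 as the expected effect. It is not: 3/7 retention is a worst case that the section 7.1 wording would not produce. The direction is not fixed either, since removing only background cases raises stopping by subject 120 from 97.1% to 99.1% (z test).

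Fourth, a reader might infer that the filter hides cases from the DSMB. It does not. Under sections 7.7 and 10.4 the DSMB is told of each confirmed case, the number of safety analyses is not limited, and evidence of net harm may end the study outside the rule. Respiratory compromise of any cause is also compared between arms under section 8.2.2.

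**Conclusion.** The point holds as a cheap improvement of low to moderate severity. The trigger in section 7.7 rests on causality ratings of single cases that a randomised comparison does not need, and the section does not say that a case with another plausible cause still counts.

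If the MSMs apply section 7.1 as worded, nearly all cases count and little changes. If they exclude cases with another cause, a HI-DEF-like pattern moves from a difference of 5, at the first limit, to at most 3. The stopping probabilities depend on assumed ARDS rates and retained fractions, so they show sensitivity and are not forecasts. The effect is confined to the pre-specified trigger.

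**What to change.** Amend section 7.7 so that the count limits and the Pocock tests use all MSM-confirmed Berlin ARDS cases by randomised arm. Give the DSMB the counts restricted to at least possibly related cases as a supplementary table, and record its agreement to the counted event.

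If the DSMB prefers to keep the filter, add one sentence to section 7.7: the section 7.1 definition governs the MSMs' rating, so a case with another plausible cause still counts.

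Either version takes about one sentence and a DSMB confirmation, with no new data. The price of counting all cases is slightly more false stops. At a 16.7% common rate the rise by subject 120 is 6.7 - 6.0 = 0.7 to 6.7 - 5.4 = 1.3 percentage points with the z test, and 4.9 - 3.9 = 1.0 to 4.9 - 3.0 = 1.9 points with Fisher, compared with retaining 6/7 or 5/7 of cases. The z-test rate for the whole rule is above 5% at all three of these counts, so the DSMB should see these figures when it confirms the rule.
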